6.5.2 Cardiovascular History

Summaries of cardiovascular history will be presented by treatment group and based on the FAS. No inferential statistics will be presented.

For each of the following cardiovascular (CV) history categories, the number and percentage of subjects will be presented: myocardial infarction (MI), hospitalized unstable angina, cardiac revascularization, cerebral revascularization, stroke, hospitalized transient ischemic attack (TIA), peripheral vascular disease (ankle brachial index ≤ 0.6), peripheral vascular disease with revascularization, peripheral vascular disease with claudication, deep vein thrombosis (DVT), pulmonary embolism (PE), history of diabetes mellitus, coronary artery bypass graft procedure, percutaneous transluminal coronary angioplasty, cardiac arrhythmia, pacemaker or defibrillator, and congestive heart failure. For subjects with a history of diabetes, a summary will also be provided by evidence of micro- or macrovascular disease (retinopathy, neuropathy, nephropathy, or small vessel vascular disease). For subjects with a history of congestive heart failure, a summary will also be provided by classification type (Class I-IV).

In addition, the number and percentage of subjects with hypertension and hyperlipidemia will be presented by treatment group.

6.5.3 Medical History and Concurrent Medical Conditions

Summaries of medical history and concurrent medical conditions will be presented by treatment group and based on the FAS. No inferential statistics will be presented.

Medical history will consist of any significant conditions or diseases that stopped at or prior to time of informed consent. Ongoing conditions will be considered concurrent medical conditions. Concurrent medical conditions are significant ongoing conditions or diseases present at time of informed consent through end of study. These include clinically significant laboratory, ECG, or physical examination abnormalities.

Medical history and concurrent medical conditions will be coded using the latest Medical Dictionary for Drug Regulatory Activities (MedDRA). The number and percentage of subjects with medical history and concurrent medical conditions will be reported by system organ class and preferred term.

6.5.4 Medication History and Concomitant Medications

Summaries of prior and concomitant medications will be presented by treatment and based on the FAS. No inferential statistics will be presented.

Any medication that was stopped prior to screening will be considered prior medication. Medication taken at any time between the date of screening and the date of last contact, inclusive, will be considered concomitant medication. Prior and concomitant medications will be coded using the World Health Organization (WHO) Drug Dictionary and will be summarized according to their anatomical therapeutic chemical classification system (ATC) classes.

The number and percentage of subjects taking prior medication and concomitant medication will be summarized separately. The table for concomitant medications will be presented in four separate components, namely: concomitant medications that stopped at or prior to baseline (Day 1); concomitant medications that were ongoing at baseline; concomitant medications that started after baseline; and concomitant medications that were ongoing at baseline or started after baseline.

Summary will be generated overall and by treatment group sorted in decreasing frequency by the overall Preferred Term. In Drug Class and Preferred Term summarizations, a subject will be counted once if the subject reports one or more medications.

6.6 Study Drug Exposure and Compliance

Summaries of study drug exposure, study participation, and compliance will be presented by treatment group and based on the FAS. No inferential statistics will be presented.

A subject's extent of drug exposure will be calculated as the duration of treatment in the double-blind treatment period. Duration of study drug exposure in days will be defined as (date of last dose - date of first dose + 1). If the date of last dose is missing and a subject has discontinued from the study, then, for summary purposes, the last dose date will be estimated as the last drug dispense date plus the number of days in the dosing interval or date of last contact, whichever comes first. The study participation will begin on the day of randomization and end on the day of last contact. Duration of study participation in days will be defined as (date of last contact - date of randomization + 1). For subjects who report a MACE event after treatment discontinuation, the start date of the event will be used as the date of last contact.

Treatment duration and study participation will be summarized overall and by treatment group using descriptive statistics and subject counts at the intervals: Day 1 to Day 364 [Year 1], Day 365 to Day 728 [Year 2], Day 729 to Day 1092 [Year 3], Day 1093 to Day 1456 [Year 4], Day 1457 to Day 1820 [Year 5], Day 1821 to Day 2184 [Year 6], and \geq Day 2185 [\geq Year 6]. In addition, within each treatment group, the duration of treatment by each dose will be summarized.

Study drug compliance will be calculated and summarized with descriptive statistics and subject counts within compliance categories (<80%, 80–<90%, \geq 90%). Compliance (%) will be calculated as the number of capsules taken divided by two times the number of days on drug.

The number and percentage of subjects on the final dose and with dose adjustment from initial dosing will be summarized by treatment group. The final doses based on sUA response and by baseline renal function are summarized in [Figure 3.a](#).

The number and percentage of subjects with use of each type of prophylactic medication based on the initial dosing and dose adjustment from initial dosing will be summarized by treatment group. In addition, descriptive statistics on the total number of days (date of last dose - date of first dose + 1) of prophylactic dosing will be summarized by treatment group.

6.7 Efficacy Analysis

Efficacy analyses will be summarized by the level of average post baseline sUA achieved using the Full Analysis Set (FAS). The FAS will consist of all subjects who were randomized and received at least one dose of double-blind study medication. The average post-baseline sUA level during the period from the end of the first year of treatment up to 1-day after a subject's last dose of study drug, will be grouped using the following categories <4.0 mg/dL, ≥ 4 to <5.0 mg/dL, ≥ 5 to <6.0 mg/dL, and ≥ 6.0 mg/dL.

Efficacy analyses will not be summarized by treatment group. Since subjects will have their dose of study drug adjusted based on sUA response, the majority of subjects will have sUA values less than 6.0 mg/dL during treatment.

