4.3 Additional Endpoints

The following are additional endpoints:

- The time from randomization to the first occurrence of any event in the pre-defined MACE composite plus any of the following events:
 - Urgent Cerebral revascularization [non-elective].
 - Hospitalized congestive heart failure (CHF).
 - Arrhythmias not associated with ischemia.
 - Venous and peripheral arterial thromboembolic events; eg, Deep Vein Thrombosis (DVT) and Pulmonary Embolism (PE).
 - Transient Ischemic Attack (TIA).
- The time from randomization to the occurrence of all-cause death.
- The time from randomization to the occurrence of all-cause death during treatment (from randomization to last dose of study medication).
- The time from last dose of study medication to the occurrence of all-cause death.
- Percentage of subjects whose average sUA levels from the end of the first year of treatment to the end of the study are <4.0 mg/dL, ≥4 to <5.0 mg/dL, ≥5 to <6.0 mg/dL, and ≥6.0 mg/dL.

- The mean number of flares requiring treatment from the end of the first year of treatment to the end of the study.
- Percentage of subjects with tophi resolution by the end of Years 1, 2, 3 and 4 for subjects with a primary palpable tophus at the Day 1 Visit.
- Other safety assessments will include:
 - Adverse events (including rash events),
 - Clinical laboratory evaluations (hematology, serum chemistry, and urinalysis),
 - Vital signs measurements (blood pressure and heart rate), and
 - Electrocardiogram (ECG) findings.

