6.0 METHODS OF ANALYSIS AND PRESENTATION

6.1 General Considerations

The SAS System with the HP-Unix operating system, will be used to perform the statistical analyses. Unless otherwise specified, all statistical tests and confidence intervals (CIs) will be two-sided and conducted at the 0.05 significance level. All computations will be performed prior to rounding. Statistical significance will be determined using p-values which have been rounded to 3 decimal places. Unless otherwise specified, descriptive statistics on continuous variables will consist of the number of subjects (N), mean, standard deviation, minimum, 25th percentile, median, 75th percentile, and maximum.

For the purpose of this document study drug will refer exclusively to the double-blind treatment namely: febuxostat (40 mg QD or 80 mg QD) or allopurinol (200 mg to 600 mg QD in 100 mg increments). Unless specified otherwise all statistical tables will be presented by febuxostat and allopurinol treatment groups with no summaries by dose.

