6.7.1 Efficacy Endpoints

There are no primary or secondary efficacy endpoints in the study. However, the following efficacy related other endpoints will be summarized.

- Percentage of subjects whose average sUA levels from the end of the first year of treatment to the end of the study are <4.0 mg/dL, ≥ 4 to <5.0 mg/dL, ≥ 5 to <6.0 mg/dL, and ≥ 6.0 mg/dL.

Average sUA will be computed based on all post-baseline sUA values collected from the end of the first year of treatment to the end of the study. For subjects with at least a year of study treatment exposure, all sUA values up to 1-day after a subject's last dose of study drug will be included in the analyses.

- The mean number of flares requiring treatment from the end of the first year of treatment to the end of the study.

The flare rate from the end of the first year of treatment (≥ 365 Days) to the end of the study will be summarized. Flare rate will be calculated as the number of flares from the end of the first year of treatment to the end of the study divided by the length of time on treatment during the period after the first year and through the end of study. The flare rate and 95% CI will be computed using Poisson regression model adjusted for treatment exposure with average sUA category as a factor in the model.

For subjects with at least a year of study treatment exposure, all flares up to 30 days after a subject's last dose of study drug will be included in the analyses.

- Percentage of subjects with tophi resolution by in Years 1, 2, 3, 4, 5, 6, and 7 for subjects with a primary palpable tophus at the Day 1 Visit.

For subjects with a primary tophus at baseline (Day 1 assessment), the percentage of subjects with tophi resolution at the end of Years 1, 2, 3, 4, 5, 6, and 7 of treatment will be summarized. The estimate for tophi resolution rate will be calculated using the life-table method. In calculating the percentage of subjects with tophi resolution, yearly intervals will be used in the life-table analysis. All tophus data up to 30 days after a subject's last dose of study drug will be included in the analyses.

The time intervals that will be used in the life table method relative to the first day of study drug and steps to calculate the resolution rate at the end of each interval are summarized in [Table 6.b](#).

Table 6.b Time Intervals and Steps to Calculate Tophus Resolution Rate

Time Interval (Years)	Interval Number	n_t	r_t	w_t	n'_t	P_t

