0 – 1	1	n_1	r_1	w_1	$n'_1 = n_1 - \frac{w_1}{2}$	$P_1 = 1 - Q_1$
1 – 2	2	$n_2 = n_1 - r_1 - w_1$	r_2	w_2	$n'_2 = n_2 - \frac{w_2}{2}$	$P_2 = 1 - Q_2$
2 – 3	3	$n_3 = n_2 - r_2 - w_2$	r_3	w_3	$n'_3 = n_3 - \frac{w_3}{2}$	$P_3 = 1 - Q_3$
3 – 4	4	$n_4 = n_3 - r_3 - w_3$	r_4	w_4	$n'_4 = n_4 - \frac{w_4}{2}$	$P_4 = 1 - Q_4$

For $t = 1, 2, 3, 4$, n_t is the number of subjects who have not had a resolved primary tophus at the beginning of the t^{th} interval, r_t is the number of subjects whose tophus resolved during the t^{th} interval, w_t is the number of subjects who were censored or lost during the t^{th} interval, n'_t is the number of subjects who have not had a resolved primary tophus at the end of the t^{th} interval adjusted for early withdrawal, and P_t is resolution rate at the end of the t^{th} interval.

$Q_t = \prod_{i=1}^t (1 - r_i/n'_i)$ is the conditional probability of no resolution at the end of the t^{th} interval, where \prod is the product notation.

In addition, the relationship between average serum urate concentration and occurrence of any gout flare requiring treatment (at least 1 occurrence versus no occurrence) from the end of the first year of treatment to the end of the study will further be evaluated using logistic regression model adjusting for baseline sUA. Descriptive summary of the baseline and average post-baseline sUA values will also be provided by occurrence of any gout flare (at least 1 occurrence versus no occurrence).

The following additional gout flare summaries will also be performed. The windows convention for the gout flare summaries by 6 month intervals [days] are: ≤ 6 [Days 2 to 182], 6-12 [Days 183 to 364], 12-18 [Days 365 to 546], 18-24 [Days 547 to 728], 24-30 [Days 729 to 910], 30-36 [Days 911 to 1092], 36-42 [Days 1093 to 1274], 42-48 [Days 1275 to 1456], 48-54 [Days 1457 to 1638], 54-60 [Days 1639 to 1820], 60-66 [Days 1821 to 2002], 66-72 [Days 2003 to 2184], 72-78 [Days 2185 to 2366], and 78-84 [Days >2366]. All flare data collected from baseline and up to 30 days after a subject's last dose of study drug will be included in the analyses.

- The number and percentage of subjects requiring treatment for gout flare will be summarized by prophylaxis medication use and overall by 6 Month intervals. A subject who reports more than one flare during the same time interval will be counted only once for that time interval.

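### Section 6.7 rules out showing sUA, flare and tophus results by randomised arm, and its stated reason does not show that the arms had similar urate control

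*SAP*

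**What the plan says.** Section 6.1 sets a default layout: "Unless specified otherwise all statistical tables will be presented by febuxostat and allopurinol treatment groups with no summaries by dose". Section 6.7 departs from it for efficacy. It opens by grouping efficacy results by the average post-baseline sUA reached, in four categories, and then states: "Efficacy analyses will not be summarized by treatment group". The reason given is that doses are adjusted on sUA response, so that "the majority of subjects will have sUA values less than 6.0 mg/dL during treatment".

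The endpoints concerned are listed in section 4.3: sUA category percentages, tophus resolution, and "The mean number of flares requiring treatment from the end of the first year of treatment to the end of the study". Section 6.7.1 describes their standing: "There are no primary or secondary efficacy endpoints in the study". It estimates the flare rate with a "Poisson regression model adjusted for treatment exposure with average sUA category as a factor in the model". The relation between average sUA and any flare "will further be evaluated using logistic regression model adjusting for baseline sUA". Neither model names randomised treatment.

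**The concern.** Randomisation gives two groups that are comparable at baseline, and section 6.7 sets that grouping aside for every on-treatment gout result. Achieved sUA is an outcome of treatment. It reflects the drug, adherence and renal function, so a difference in flares or tophi between sUA categories cannot be read as an effect of treatment.

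The trial compares two urate-lowering drugs on MACE. Section 6.13 adds that it continued to 624 events to assess all-cause and CV mortality. A reader of those comparisons will want to know whether urate control and gout burden were alike in the two arms. Under this plan no table answers that directly.

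**Working it through.** The point disputes no figure in the plan. The check is whether any section restores a by-arm result, whether the stated reason holds, and whether a by-arm table would be informative.

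**1. What each analysis is grouped by (sections 6.7 and 6.7.1)**
- sUA category percentages: grouped by achieved sUA, which for this endpoint amounts to one pooled distribution.
- Flare rate after Year 1: sUA category is the only factor in the Poisson model.
- Any flare after Year 1: average sUA, adjusted for baseline sUA.
- Tophus life table: falls under the section 6.7 rule, so by achieved sUA.
- Six-month flare tables: by prophylaxis use and overall, or as a rate per subject-year.
- Flare signs and symptoms: by sign and severity.

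None is by randomised arm.

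**2. Whether another section fills the gap**
- Section 6.5.1 gives baseline urate and gout history by arm. These are pre-treatment.
- Section 6.6 gives final dose, dose adjustment, time at each dose and compliance by arm. These are indirect.
- Section 6.12.5 summarises serum chemistry by visit but does not name sUA, and Appendix A does not list it.

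No on-treatment sUA, flare or tophus result by arm is restored.

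**3. Whether the stated reason holds**

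A pooled majority below 6.0 mg/dL is compatible with unequal arms. With 1:1 allocation, 50% in one arm and 90% in the other would pool to (50 + 90)/2 = 70%. Section 3.2 gives no ground to assume equality:
- Febuxostat has one possible step, from 40 to 80 mg.
- Allopurinol has up to (600 − 300)/100 = 3 steps, or (400 − 200)/100 = 2 in moderate renal impairment.
- Both are capped, and adjustment ends at Month 3. The sUA endpoint starts at the end of Year 1, 12 − 3 = 9 months later.

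The plan also divides values below 6.0 mg/dL into three categories, so it treats differences in that range as worth reporting.

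**4. A timing problem in the replacement grouping**

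Average sUA is computed from values after the first year, whereas the tophus life table starts on the first day of drug. A subject who stops drug within the first year has no category. Year 1 resolution would therefore be classified by a later measurement, in those who stayed on drug.

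**5. Precision of a by-arm sUA table**

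Input from section 5.0: 3750 per arm. Assumptions, since the SAP gives no figures: a fraction r = 0.5 to 0.9 of each arm has at least a year on drug, and a proportion p = 0.5 to 0.9 of those averages below 6.0 mg/dL. With n = 3750r, the 95% half-width for the difference is 1.96 × √(2p(1 − p)/n).
- Least favourable (r = 0.5, p = 0.5): n = 1875; 1.96 × √(0.50/1875) = 0.0320, or 3.2 points.
- Most favourable (r = 0.9, p = 0.9): n = 3375; 1.96 × √(0.18/3375) = 0.0143, or 1.4 points.

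Lack of precision therefore cannot justify the omission.

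**The case against.** This is a CV safety trial, and section 6.7.1 gives these endpoints neither primary nor secondary status. The choice is deliberate and disclosed, and it touches no alpha, sample size or primary test. The Cox model in section 6.12.1 compares randomised arms whatever urate was achieved, and achieved urate is itself a consequence of treatment. Section 6.6 shows final dose by arm, and since dose follows sUA this is an indirect view of early response. Section 6.4 compares discontinuation by arm. All of this stands and limits the weight of the point. None of it supplies long-term sUA, flare or tophus results by arm, and none rescues the stated reason.

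A further objection concerns what by-arm tables could deliver. Average sUA and the post-Year-1 flare rate are defined for subjects with at least a year of exposure. A by-arm comparison of them would still be restricted to subjects selected after randomisation. This is correct, and the tables should say so. The tophus life table and the six-month flare tables carry no such entry restriction.

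**Conclusion.** The point holds as a moderate defect in the analysis of additional endpoints. No on-treatment result for sUA, flares or tophi is shown by arm, and the reason given does not support leaving it out. The textual finding rests on no assumption. The 1.4 to 3.2 point half-width rests on the assumed ranges in the working.

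Four stronger readings are tempting, and the SAP does not support them:
- A reader might infer that a by-arm table would be fully unconfounded. For average sUA and the post-Year-1 flare rate it would condition on a year on drug.
- A reader might infer that every efficacy table is grouped by achieved sUA. The additional flare tables are not.
- A reader might apply the 10% annual drop-out in section 5.0 to count subjects without an sUA category. That rate is an assumption for the MACE sample size and is not equated with stopping drug. A by-arm table of the same endpoint would also lose the same subjects, so the count does not measure this defect.
- A reader might infer that the MACE hazard ratio cannot be interpreted without these tables. They help explain it, but nothing in the non-inferiority test depends on them.

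**What to change.** - In section 6.7, replace the sentence excluding treatment-group summaries. The new rule: sUA category percentages, flare rate, six-month flare tables and the tophus life table are also presented descriptively by randomised arm, with 95% CIs, no alpha, and stratification by baseline renal function where a model is used.
- Amend the opening sentence of section 6.7 to match. Deleting the exclusion alone would leave grouping by achieved sUA as the governing rule.
- In section 6.7.1, add a Poisson flare model with randomised treatment as the factor.
- State per arm how many FAS subjects have no average sUA because they had less than a year on drug.
- Note that the sUA and post-Year-1 flare-rate comparisons condition on staying on drug, and that the tophus and six-month flare tables have no such entry restriction.
- Keep the achieved-sUA analyses, labelled exploratory.

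The cost is a few extra tables and one model from data already collected. Sample size, alpha and the primary analysis are unchanged.

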6.7.1 Efficacy Endpoints

There are no primary or secondary efficacy endpoints in the study. However, the following efficacy related other endpoints will be summarized.

- Percentage of subjects whose average sUA levels from the end of the first year of treatment to the end of the study are <4.0 mg/dL, ≥ 4 to <5.0 mg/dL, ≥ 5 to <6.0 mg/dL, and ≥ 6.0 mg/dL.

Average sUA will be computed based on all post-baseline sUA values collected from the end of the first year of treatment to the end of the study. For subjects with at least a year of study treatment exposure, all sUA values up to 1-day after a subject's last dose of study drug will be included in the analyses.

- The mean number of flares requiring treatment from the end of the first year of treatment to the end of the study.

The flare rate from the end of the first year of treatment (≥ 365 Days) to the end of the study will be summarized. Flare rate will be calculated as the number of flares from the end of the first year of treatment to the end of the study divided by the length of time on treatment during the period after the first year and through the end of study. The flare rate and 95% CI will be computed using Poisson regression model adjusted for treatment exposure with average sUA category as a factor in the model.

For subjects with at least a year of study treatment exposure, all flares up to 30 days after a subject's last dose of study drug will be included in the analyses.

- Percentage of subjects with tophi resolution by in Years 1, 2, 3, 4, 5, 6, and 7 for subjects with a primary palpable tophus at the Day 1 Visit.

For subjects with a primary tophus at baseline (Day 1 assessment), the percentage of subjects with tophi resolution at the end of Years 1, 2, 3, 4, 5, 6, and 7 of treatment will be summarized. The estimate for tophi resolution rate will be calculated using the life-table method. In calculating the percentage of subjects with tophi resolution, yearly intervals will be used in the life-table analysis. All tophus data up to 30 days after a subject's last dose of study drug will be included in the analyses.

The time intervals that will be used in the life table method relative to the first day of study drug and steps to calculate the resolution rate at the end of each interval are summarized in [Table 6.b](#).

Table 6.b Time Intervals and Steps to Calculate Tophus Resolution Rate

Time Interval (Years)	Interval Number	n_t	r_t	w_t	n'_t	P_t
0 – 1	1	n_1	r_1	w_1	$n'_1 = n_1 - \frac{w_1}{2}$	$P_1 = 1 - Q_1$
1 – 2	2	$n_2 = n_1 - r_1 - w_1$	r_2	w_2	$n'_2 = n_2 - \frac{w_2}{2}$	$P_2 = 1 - Q_2$
2 – 3	3	$n_3 = n_2 - r_2 - w_2$	r_3	w_3	$n'_3 = n_3 - \frac{w_3}{2}$	$P_3 = 1 - Q_3$
3 – 4	4	$n_4 = n_3 - r_3 - w_3$	r_4	w_4	$n'_4 = n_4 - \frac{w_4}{2}$	$P_4 = 1 - Q_4$

For $t = 1, 2, 3, 4$, n_t is the number of subjects who have not had a resolved primary tophus at the beginning of the t^{th} interval, r_t is the number of subjects whose tophus resolved during the t^{th} interval, w_t is the number of subjects who were censored or lost during the t^{th} interval, n'_t is the number of subjects who have not had a resolved primary tophus at the end of the t^{th} interval adjusted for early withdrawal, and P_t is resolution rate at the end of the t^{th} interval.

$Q_t = \prod_{i=1}^t (1 - r_i/n'_i)$ is the conditional probability of no resolution at the end of the t^{th} interval, where \prod is the product notation.

In addition, the relationship between average serum urate concentration and occurrence of any gout flare requiring treatment (at least 1 occurrence versus no occurrence) from the end of the first year of treatment to the end of the study will further be evaluated using logistic regression model adjusting for baseline sUA. Descriptive summary of the baseline and average post-baseline sUA values will also be provided by occurrence of any gout flare (at least 1 occurrence versus no occurrence).

The following additional gout flare summaries will also be performed. The windows convention for the gout flare summaries by 6 month intervals [days] are: ≤ 6 [Days 2 to 182], 6-12 [Days 183 to 364], 12-18 [Days 365 to 546], 18-24 [Days 547 to 728], 24-30 [Days 729 to 910], 30-36 [Days 911 to 1092], 36-42 [Days 1093 to 1274], 42-48 [Days 1275 to 1456], 48-54 [Days 1457 to 1638], 54-60 [Days 1639 to 1820], 60-66 [Days 1821 to 2002], 66-72 [Days 2003 to 2184], 72-78 [Days 2185 to 2366], and 78-84 [Days >2366]. All flare data collected from baseline and up to 30 days after a subject's last dose of study drug will be included in the analyses.

- The number and percentage of subjects requiring treatment for gout flare will be summarized by prophylaxis medication use and overall by 6 Month intervals. A subject who reports more than one flare during the same time interval will be counted only once for that time interval.

- The total number of flares and the flare rate per subject year of treatment exposure will be summarized by 6 month intervals. Within the time intervals, subject year is the total number of days of drug exposure for all subjects with exposure for the interval divided by 365.
- The number and percentage of subjects requiring treatment for gout flare will also be summarized by signs and symptoms of gout flare (Swelling, Redness, Tenderness, Joint Warmth, and Other Signs/Symptoms).

If a subject reports more than one signs and symptoms category, then for summary purpose the subject will be counted within each reported signs and symptoms category. However, if a subject reports the same signs and symptoms more than once during the study period then the subject will be counted only once in that category. Summary in each signs and symptoms category will also be provided by severity level (Mild, Moderate, Severe). If a subject reports different severity level for the same signs and symptoms category during the study period, the most severe level will be used for summary purposes.

